### Study summary

This subject-masked, randomised, bilateral crossover study will compare the clinical performance and subjective acceptance of the clariti 1day soft contact lens with the DAILIES AquaComfort Plus lens when used on a daily wear, daily disposable basis.

Seventy subjects will be enrolled on this study and will wear each lens brand for one week in random sequence. The following will be assessed throughout the study: ocular physiology, [redacted] ocular redness, [redacted] and subjective response.

A study summary is shown in Table 1.

Visit	Procedures
Information presentation Dispensing 1	Short one presentation of study aims and procedures Informed consent taken Explanation of study procedures and subject instructions Ocular and contact lens history [redacted] Autokeratometry Ocular redness assessment Biomicroscopy Fitting of study lens pair 1 [redacted] Subjective scores Issue study lenses and diary
Follow-up 1 / Dispensing 2	[redacted] [redacted] [redacted] Removal of lens pair 1 [redacted] Ocular redness assessment Biomicroscopy Fitting of study lens pair 2 [redacted] [redacted] [redacted]
Follow-up 2	[redacted] [redacted] [redacted] Removal of lens pair 2 [redacted] Ocular redness assessment Biomicroscopy [redacted] Exit form signed [redacted]

Table 1: Study summary.

## Section 1. Overview

### 1.1 Background

This project seeks to compare the clinical performance of the clariti 1day lens (CooperVision Inc.) with the DAILIES AquaComfort Plus lens (Alcon Inc.).

### 1.3 Study objectives

This study aims to compare the clinical performance of the clariti 1day lens with the DAILIES AquaComfort Plus lens.

### 1.4 Study design

This will be a randomised, subject-masked, crossover, bilateral study, controlled by cross-comparison. Seventy subjects will use each lens type for a week in random sequence. Follow-up visits for each lens will be performed after one week of wear. Lenses will be worn on a daily wear, daily disposable wear schedule.

### 1.5 Statistical considerations

The principal hypothesis to be tested in this work is that biomicroscopic and subjective scores for the lenses will be substantially equivalent.

[REDACTED] biomicroscopy, ocular redness, [REDACTED] and subjective responses will generate data that are likely to be continuous and normally distributed. As such, these will be compared using linear regression models or other parametric methods. Subjective preferences will be compared using chi-squared tests.

[REDACTED]  
Deviations from this statistical plan will be discussed in the final report. Deviations may be necessary due to differences between the actual data distribution compared with the anticipated data distribution.

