#### 1.5.1 Power analysis

Assessment using a dataset from a similar, previous study found that a power of 0.8 or greater is provided by 65 completing subjects for the following measures: subjective comfort at lens dispensing, subjective comfort at the start and end of the day, overall subjective comfort, subjective vision, [REDACTED] and for the following biomicroscopic signs: conjunctival and limbal redness, corneal staining, conjunctival staining and papillary

conjunctivitis. This analysis assumes a two-tailed paired analysis and an alpha of 0.05. To allow for discontinuations, 70 subjects will be recruited.

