#### 3.2.2 Dispensing 1 visit

The subject will have received a study-specific information form outlining the study at least 24 hours before the consent visit, and will then be required to sign an informed consent form prior to enrolment [REDACTED]. A copy of the signed form will be issued to the subject. When the subject has signed the consent form, they are considered to be enrolled on the study.

Subjects will be instructed on the following:

1. Lens handling, application and removal, where necessary.
2. Specific study instructions, such as the importance of not using any other contact lens products.
3. General contact lens information such as the management of red eyes.

The following procedures will be performed (any ocular measurement procedures outlined below will be carried out on each eye):

1. Details of the ocular and medical histories and contact lens-wearing history of the subject will be noted [REDACTED]
2. [REDACTED]
3. [REDACTED]
4. [REDACTED]
5. Slit lamp biomicroscopy will be carried out for the signs outlined in Table 4 and in accordance with the current Eurolens Research Standard Operating Procedure 'Examination of the anterior segment using slit lamp biomicroscopy'. Grades will be scored to the nearest 0.1 unit in the best judgement of the investigator using Efron Grading Scales. Corneal staining will be graded for five regions (central, superior, temporal, inferior and nasal) as well as an 'overall' grade. The predominant type of corneal staining present will also be recorded.

Classification	Primary signs	Secondary signs
Signs	Conjunctival redness Limbal redness [REDACTED] Corneal staining [REDACTED] Conjunctival staining Conjunctival indentation Papillary conjunctivitis	Blepharitis Meibomian gland dysfunction Mucous bands
Score	Efron Grading Scales (scored to nearest 0.1)	Efron Grading Scales (scored to nearest 0.1) (except mucous bands, where the number is recorded).

Table 4: Biomicroscopic signs. Staining assessed with sodium fluorescein.

The presence of any ocular adverse events will be recorded, and reported as appropriate [REDACTED]

6. The investigator will confirm that the subject satisfies all the inclusion and exclusion criteria. Subjects who fail to meet all the criteria at this time will usually be discontinued and replaced. If in the opinion of the investigator, the subject may be eligible at a later date, the subject may be brought back for up to ONE repeat visit of this type.

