### **3.4 Missing, unused and spurious data**

The absence of any data will be carefully and critically considered. If appropriate, partial datasets will be included in the final analysis. Any data missing from a subject visit will be outlined in the report by indicating the number of subjects included for each analysis. Data that are unused or considered to be spurious will be detailed and discussed in the report.

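### Does section 1.5 need to name the unit of analysis and a subject term before a paired analysis of this two-eye crossover is secured?

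*Combined protocol and SAP*

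**What the plan says.** Section 1.4 sets the design: "This will be a randomised, subject-masked, crossover, bilateral study, controlled by cross-comparison". Section 3.2.2 adds that "any ocular measurement procedures outlined below will be carried out on each eye", so an ocular sign gives up to four post-wear values per subject, two eyes under each of two lenses. The visual analogue scores in sections 3.2.2 and 3.2.3 are given by the subject, with no visible mention of scoring by eye.

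The visible sentence on analysing continuous outcomes, in section 1.5, is "As such, these will be compared using linear regression models or other parametric methods". A redacted block follows shortly after it, before the remark on deviations from the statistical plan.

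Section 1.5.1, a subsection of 1.5, states that "a power of 0.8 or greater is provided by 65 completing subjects" for its listed measures, and then: "This analysis assumes a two-tailed paired analysis and an alpha of 0.05". Section 3.4 promises to report missing data by "indicating the number of subjects included for each analysis".

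**The concern.** The word for pairing appears only in the sample-size paragraph. The analysis sentence could be met by a regression on lens alone, by a regression with a subject effect, or by a model in which each eye is a separate row. These do not give the same inference.

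Two things could go wrong. Ignoring the pairing would give up the power that section 1.5.1 relies on. Keeping the pairing but entering both eyes as independent rows would understate the standard error whenever a subject's eyes respond alike to a change of lens. The principal hypothesis in section 1.5 is one of equivalence, so intervals that are too narrow would favour the conclusion the study hopes to reach.

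**Working it through.** **The plan's own figure.** Inputs from section 1.5.1: 65 completers, power at least 0.8, two-sided alpha 0.05, paired. No effect size, standard deviation or correlation is visible, so 65 cannot be reproduced, only back-solved. In normal form the detectable standardised paired difference is (1.960 + 0.842)/√65 = 2.802/8.062 = 0.347; with the t distribution on 64 degrees of freedom it is 0.353. The move from 65 to 70 implies an allowance of 5/70 = 7.1%, and 65/(1 − 0.0714) = 70. The figures fit a subject-level paired analysis.

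**If the pairing were dropped** (one score per subject and lens). With correlation r between a subject's two scores, the unpaired standard error is the true one divided by √(1 − r). The critical value on the true scale is therefore 1.960/√(1 − r), against an expected statistic of 0.3528 × 8.062 = 2.844. All r are assumed.

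| r | Critical value | Power, formula | Power, simulated |
|---|---|---|---|
| 0.3 | 2.343 | Φ(0.50) = 0.69 | 0.68 |
| 0.5 | 2.772 | Φ(0.07) = 0.53 | 0.52 |
| 0.7 | 3.578 | Φ(−0.73) = 0.23 | 0.23 |

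These figures hold for an outcome whose paired power is exactly 0.80, which section 1.5.1 gives as a floor. For an outcome with paired power 0.95, the simulated unpaired power is 0.90, 0.80 and 0.52.

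**If the pairing were kept but eyes treated as independent.** Let ρ be the correlation between a subject's two eyes in their lens differences. The standard error from 130 eye-level differences is too small by the factor 1/√(1 + ρ), so the true type I error is 2[1 − Φ(1.960/√(1 + ρ))]. All ρ are assumed.

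| ρ | 1.960/√(1 + ρ) | Type I error | Simulated |
|---|---|---|---|
| 0 | 1.960 | 0.050 | 0.051 |
| 0.25 | 1.753 | 0.080 | 0.079 |
| 0.5 | 1.600 | 0.110 | 0.110 to 0.113 |
| 0.75 | 1.482 | 0.138 | 0.139 to 0.140 |

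Averaging the eyes per subject and lens gave 0.049 to 0.050 in the same simulations.

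**Which of these does the plan leave open?** The first case requires the team to set aside the paired assumption on which it sized the study. The second is not expressly excluded, but sections 1.5.1 and 3.4 both count subjects, not eyes. It can apply only to outcomes graded by eye. Of the ten measures visibly listed in section 1.5.1, five are subjective scores and five are biomicroscopic signs, so the eye question reaches the latter five.

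**The case for a change.** The best argument for a change is that a sample-size assumption does not bind the analysis. Even if section 1.5.1 is read as a commitment, it does not choose between pairing by subject and pairing by eye, and eye-level pairing is the version that inflates error. A competent analyst could also go wrong here. A mixed model with eye nested in subject looks adequate, yet its standard error matched that from 130 independent eye-level differences (median ratio 1.000 over 80 simulated datasets). A subject-by-lens effect is needed to recover the eye-mean standard error; subject-clustered standard errors would also address the dependence. Under a margin-based test, the nested model would claim equivalence at the margin with probability about 0.09 and 0.11 at ρ of 0.5 and 0.75, against a nominal 0.05. One added sentence would remove the doubt.

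The arithmetic stands, and so does the observation that the visible text does not say how eyes are combined. The case for amendment is weaker. Every correlation is assumed. The visible plan states neither an equivalence margin nor a one-sided test, so the false-equivalence figures illustrate a procedure it does not describe. The redacted block is a natural place for model terms, and text removed from the public copy cannot be counted as absent. A model with lens, period and subject is one instance of the linear regression already named, so writing it in would add detail without correcting an error. Period and sequence terms are a separate choice, not needed to restore pairing.

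**Conclusion.** The sentence in section 1.5 is under-specified, not wrong. It allows the correct analysis, and the design, the paired power basis and the counting by subject all point to it. The loss of power to 0.68, 0.52 or 0.23 would arise only if the team contradicted its own section 1.5.1.

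The open detail is how two eyes enter the analysis of the ocular signs. If it were handled badly, type I error would be about 0.08 to 0.14 for assumed inter-eye correlations of lens differences of 0.25 to 0.75, with no inflation at zero correlation. Analysts ordinarily fill this gap with one value per subject and lens, or with an eye-level model that allows for within-subject correlation of the lens differences; either is within the plan as written. A reader of the final report should check which was done. No amendment is called for. This conclusion rests on reading 1.5 together with 1.5.1 and 3.4, and on not treating redacted text as missing.

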#### 1.5.1 Power analysis

Assessment using a dataset from a similar, previous study found that a power of 0.8 or greater is provided by 65 completing subjects for the following measures: subjective comfort at lens dispensing, subjective comfort at the start and end of the day, overall subjective comfort, subjective vision, [REDACTED] and for the following biomicroscopic signs: conjunctival and limbal redness, corneal staining, conjunctival staining and papillary

conjunctivitis. This analysis assumes a two-tailed paired analysis and an alpha of 0.05. To allow for discontinuations, 70 subjects will be recruited.

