#### 2.1.1 Subject withdrawal and replacement

This study includes three clinical visits. Once the study consent form is signed, the subject is considered to be enrolled on the study. Subjects who have signed the consent form, but who have not completed the dispensing visit will usually be replaced. All subject data will be included in the final analyses unless there are strong grounds for exclusion; such grounds will be detailed in the final report. At the end the study, all subjects will sign a study exit form.

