#### 2.2 Subject discontinuation

In general, subjects should be discontinued at any time, if it is in their best interests, as judged by the investigator. Reasons for this may include clinical signs of grade 3 or more, lack of motivation, discomfort, repeated refusal to follow instructions or the use of non-study products such as solutions or lenses. Subjects will be discontinued if a serious adverse event occurs or if they miss two or more planned consecutive visits. Subjects who fail to satisfy all the inclusion and exclusion criteria will be discontinued and replaced. Subjects may choose to leave the study at their own request. All discontinuations will be carefully recorded.

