#### 3.1.1 Unscheduled visits

Subjects who attend at their own volition, (or as instructed to do so by the investigator) rather than for a scheduled study visit, will be examined and the visit will be classified as 'unscheduled'. Data collected at these visits will be recorded on the clinical study database.

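### Do sections 1.5.1, 2.1.1 and 3.4 set conflicting rules for a subject with data on only one lens?

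*Combined protocol and SAP*

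**What the plan says.** Section 1.5.1 reports, from an earlier similar dataset, that "a power of 0.8 or greater is provided by 65 completing subjects for the following measures", and adds: "This analysis assumes a two-tailed paired analysis and an alpha of 0.05". Recruitment is set at 70 to cover discontinuations.

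Section 1.5 gives the principal hypothesis, that "biomicroscopic and subjective scores for the lenses will be substantially equivalent". It names linear regression or another parametric method for the scores. Part of the section is blacked out.

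Two passages deal with incomplete data. Section 2.1.1: "All subject data will be included in the final analyses unless there are strong grounds for exclusion", with the grounds to be given in the final report. Section 3.4: "If appropriate, partial datasets will be included in the final analysis". Section 3.4 also requires the report to give the number of subjects in each analysis and to discuss data left unused.

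Section 2.2 says of discontinuation: "Reasons for this may include clinical signs of grade 3 or more, lack of motivation, discomfort". It requires every discontinuation to be recorded. Section 3.1.1 says of unscheduled visits: "Data collected at these visits will be recorded on the clinical study database".

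**The concern.** A paired test cannot use a subject with a score on one lens only. Section 1.5.1 therefore seems to exclude such a subject, section 2.1.1 to include them by default, and section 3.4 to leave the matter to judgement once the missing data are known.

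The subjects affected may not be a random subset. Discomfort and high-grade signs are possible reasons for stopping, and comfort and graded signs are the outcomes compared. If more subjects stop on the worse lens, a completers-only analysis pulls the estimated difference towards zero. That makes equivalence easier to claim and a true difference harder to detect.

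**Working it through.** **The planned size.** The 65 cannot be reproduced, because the visible text gives no effect size, SD or margin. It can be inverted. With a paired t-test, two-sided alpha 0.05 and n = 65, power 0.80 corresponds to a difference of (1.960 + 0.842)/√65 = 0.347 SD of the paired difference by the normal approximation, or 0.353 SD by the noncentral t. The standard error is 1/√65 = 0.124 SD. The allowance is 70 − 65 = 5 subjects, or 5/70 = 7.1%.

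**Completers against full data on all 70.** Let g be how far a stopped subject's paired difference lies from that of completers, in SDs of the difference. Let *net* be the excess of stops on the worse lens. Completers then miss s = net × g/70. Neither g nor the split is in the documents, so both are assumed over a range. Power is taken at a true difference of 0.353 − s. False equivalence is the chance that a one-sided 0.05 test passes when the true difference lies on the margin (noncentrality s√65, other bound not in play).

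| Split of 5 stops (net) | g | s | Power | False equivalence |
|---|---|---|---|---|
| 3:2 (1) | 1 | 0.014 | 0.77 | 0.06 |
| 3:2 (1) | 2 | 0.029 | 0.73 | 0.08 |
| 3:2 (1) | 3 | 0.043 | 0.69 | 0.10 |
| 4:1 (3) | 1 | 0.043 | 0.69 | 0.10 |
| 4:1 (3) | 2 | 0.086 | 0.56 | 0.17 |
| 4:1 (3) | 3 | 0.129 | 0.43 | 0.27 |
| 5:0 (5) | 1 | 0.071 | 0.61 | 0.14 |
| 5:0 (5) | 2 | 0.143 | 0.39 | 0.31 |
| 5:0 (5) | 3 | 0.214 | 0.20 | 0.53 |

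With an even split or g = 0, s = 0. The benchmark here is two-lens data on all 70, which no inclusion rule can supply for a subject who never wore the second lens.

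**What the choice of rule changes.** The relevant comparison is dropping against keeping the one-lens scores. Take 65 pairs plus five first-period scores on one lens, in a model with lens, period and random subject. The estimate moves, per unit g, by 0.048, 0.035 or 0.021 SD for a between-lens correlation of 0.3, 0.5 or 0.7. The full shift per unit g is 5/70 = 0.071, so about 67%, 49% or 29% is recovered (0.048, 0.035 and 0.021 over 0.0714).

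- At g = 2 the movement is 0.096, 0.070 or 0.042 SD, all below the standard error of 0.124.
- At g = 3 it is 0.144, 0.105 or 0.063 SD, above one standard error only at the lowest correlation.

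This assumes a 5:0 split, every stop in week one, and a score on the offending lens for each subject. A week-two stop has follow-up scores for the first lens. For the second it may have only dispensing scores, so keeping that subject recovers less.

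**Precision.** In the same model, five one-lens subjects raise the effective number of pairs from 65 to between 65.2 (correlation 0.9) and 66.7 (correlation 0.3), and power from 80.0% to between 80.1% and 81.1%. The sample size is unaffected.

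**The passages side by side.** The word *analysis* in the sentence quoted from 1.5.1 means the power analysis. Sizing on completers is compatible with analysing everyone. Section 1.5 admits a model that uses single-period scores. Section 2.1.1 is the general rule and 3.4 the particular one for absent data. Each is conditional, and neither forbids what the other requires.

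**The case for a change.** The best argument for a change is that the defaults differ: 2.1.1 needs strong grounds to exclude, while 3.4 needs a judgement to include, with no criterion. The methods allowed by 1.5 also cover a paired t-test or a regression with fixed subject effects, in which one-lens subjects contribute nothing, so two analysts could report different estimates. The gain in precision is beside the point, since the worry is bias, and the bias favours the principal hypothesis.

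Much of this stands. The criterion is missing, the direction of bias is as described, and the small power gain does not answer it. But an analyst who follows 2.1.1 and keeps the data is not led to a wrong result. One who leaves data out must give the grounds, show the number in each analysis and discuss what was unused. With discontinuations recorded as well, an omission would be visible.

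One possible remedy is to count scores from the stopping visit, scheduled or not, as that lens's result. This is open to dispute. Such a visit may fall outside the 6 to 10 day window in Table 3 or fail the two-hour wear condition, and 3.1.1 does not say that subjective scores are taken there.

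**Conclusion.** There is no three-way conflict. Section 1.5.1 is a planning assumption, and 2.1.1 and 3.4 can be applied together. What remains is that 3.4 gives no criterion for including partial data, a gap analysts would sensibly fill by following 2.1.1 and analysing all available lens scores.

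The choice between keeping and dropping one-lens scores moves the estimate by 0.04 to 0.10 SD when all five stops occur in week one on one lens with g = 2, less than one standard error. It shrinks with a more even split, a smaller g or a higher correlation. The larger losses in the table, down to power 0.20, need a 5:0 split and g = 3 and are measured against data that no rule can produce. These sizes rest on assumed values of g, split and correlation, and on five stops, which is a recruitment allowance and not a forecast. The blacked-out text in 1.5 may already name the model. No change to the plan is needed.

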## **1.6 Risk analysis**

This study is considered to be a non-significant risk study based on United State Food and Drug administration (FDA) and International Standards Organization (ISO) guidelines due to the daily wear nature of the study. With the potential benefit of this study, the work is considered to be ethically justifiable. Ethical approval will be sought from the University of Manchester Senate Committee on the Ethics of Research on Human Beings (hereafter referred to as Manchester UREC). The work where practical will be conducted in accordance with the ICH Good Clinical Practice Guidelines and the international standard BS EN ISO 14155:2011 'Clinical investigation of medical devices for human subjects'.

## Section 2. Resources

### 2.1 Subject selection

In this work 70 subjects will be recruited and enrolled.

#### 2.1.1 Subject withdrawal and replacement

This study includes three clinical visits. Once the study consent form is signed, the subject is considered to be enrolled on the study. Subjects who have signed the consent form, but who have not completed the dispensing visit will usually be replaced. All subject data will be included in the final analyses unless there are strong grounds for exclusion; such grounds will be detailed in the final report. At the end the study, all subjects will sign a study exit form.

